	
lead to an improvement in Clinical COPD Questionnaire (CCQ) overall score and the three subdomains: symptoms (4 items), functional state (4 items) and mental state (2 items) during a study period of approximately 8 weeks.
 
Primary objective:
 
• To assess proportion of patients achieving 0.2 points decrease in the CCQ score* between baseline (visit 1 = visit at the start of the study) and after approximately 8 weeks of treatment (visit 2) in patients with high CCQ baseline score (≥ 2) 
*CCQ score means the CCQ overall score, unless otherwise stated
 
Secondary objectives:
 
• To assess proportion of patients achieving 0.2 points decrease in the CCQ score between baseline (visit 1) and after approximately 8 weeks of treatment (visit 2) in patients independently from CCQ baseline score• To assess the mean change in CCQ score and in the scores of the 3 CCQ subdomains, symptom, mental state, and functional state domain in all patients independently from CCQ baseline score between baseline (visit 1) and after approximately 8 weeks of treatment (visit 2)• To assess the mean change in CCQ score and in the scores of the CCQ subdomains symptom, mental state, and functional state domain in patients with high CCQ baseline score (≥ 2) between baseline (visit 1) and after approximately 8 weeks of treatment (visit 2)• To assess patients' breathlessness based on modified Medical Research Council (mMRC) score at baseline (visit 1) and after approximately 8 weeks of treatment (visit 2)• To assess the change in mMRC score between baseline (visit 1) and after approximately 8 weeks of treatment (visit 2)
Country(-ies) of study:	Approximately 225 COPD patients from Switzerland
Author:	
Date:	03 Mar 2022
Page 1 of 51	
Proprietary confidential information © 2022 Boehringer Ingelheim Group of companies. All rights reserved. This document may not - in full or in part - be passed on, reproduced, published or otherwise used without prior written permission	

HRQoL	Health Related Quality of Life
ICH	International Conference on Harmonization

i. e.	Id Est
IEC	Independent Ethics Committee
IPCRG	International Primary Care Respiratory Group
IRB	Institutional Review Board
ISF	Investigator Site File
LABA	Long acting beta ₂ adrenoceptor agonist
LAMA	Long-acting muscarinic antagonist
m	Male
MAH	Marketing Authorization Holder
Max	Maximum
MedDRA	Medical Dictionary for Drug Regulatory Activities
Min	Minimum
mMRC	Modified Medical Research Council
n	Number (quantity)
NIS	Non-Interventional Study
NIS-DMRP	NIS-Data Management and Review Plan
PFIR	Peak Inspiratory Flow Rate
SADR	Suspected Adverse Drug Reaction
SAE	Serious Adverse Event
SAP	Statistical Analysis Plan
SD	Standard Deviation
SDV	Source Data Verification
SMI	Soft Mist Inhaler
SmPC	Summary of product characteristics
SOP	Standard Operating Procedure
w	week
WHO	World Health Organization

3. ABSTRACT

Name of company: Boehringer Ingelheim			
Name of finished medicinal product: Spiriva® HandiHaler® and Spiriva® Respimat®			
Name of active ingredient: Tiotropium bromide			
Protocol date: 03 Mar 2022	Study number:	Version/Revision: 1.0	Version/Revision date:
Title of study:	Switching COPD Patients from Spiriva® HandiHaler® maintenance therapy to Spiriva® Respimat®: a non- Interventional Real-world clinic Al ou T come ass Ess ment: NIS PIRATE		
Rationale and background:	
Chronic obstructive pulmonary disease (COPD) is a common and serious condition, characterized by persistent respiratory symptoms and airflow limitation. Giving to the GOLD 2021 strategy report, long-acting bronchodilators such as long-acting muscarinic antagonists and long-acting β2-agonists are the basis of maintenance therapy for patients with moderate-to-very severe COPD.
 
Beside the pharmacological compound, matching each patient with the most appropriate inhaler is important for an optimal inhaler technique and drug delivery. Previous studies suggested that COPD patients with suboptimal peak inspiratory flow rate (PIFR) may not achieve the greatest possible drug deposition and efficacy when using a dry powder inhaler (DPI) for delivery of inhalative COPD medication.
 
The Respimat®, an active soft-mist inhalation device, allows COPD patients to inhale without effort and can be used irrespective of the PIFR a patient can generate.
 
This NIS aims to evaluate whether patients will benefit from the switch from the DPI Spiriva® HandiHaler® to the Spiriva® Respimat® device, which the physician decides based on the needs of the patient prior to study inclusion using the Clinical COPD Questionnaire (CCQ) and its three domains, changes in clinical control will be assessed.
 
Note: Patients will be included into the study independently of their CCQ* score at baseline.
 
*CCQ score means the CCQ overall score, unless otherwise stated
		
Research question and objectives:	
The objective of this NIS is to test whether changing COPD patients from a dry powder inhaler (HandiHaler®) to a soft mist inhaler (Respimat®), without changing the pharmacological compound, will lead to an improvement in Clinical COPD Questionnaire (CCQ) score (covering last 7 days prior to visit) and in the scores of the three subdomains: symptoms (4 items), functional state (4 items) and mental state (2 items) during a study period of approximately 8 weeks.
		

The primary objective of the NIS is to assess proportion of patients achieving 0.2 points decrease in the CCQ score between baseline and after approximately 8 weeks of treatment) in patients with high CCQ baseline score (≥ 2).

Secondary objectives of the NIS are the assessment of the proportion of patients achieving 0.2 points decrease in the CCQ score between baseline and after approximately 8 weeks of treatment independently from CCQ baseline score, the mean change in CCQ score and in the three CCQ domains symptom, mental state, and functional state domain in all patients and in patients with high CCQ baseline score (≥ 2) between baseline and visit 2 (approximately at week 8 after visit 1), breathlessness based on modified Medical Research Council (mMRC) score at baseline, visit 2 (approximately at week 8 after visit 1), change in mMRC score between baseline and visit 2 (approximately at week 8 after visit 1).

Safety data on COPD patients switching from Spiriva® HandiHaler® to Spiriva® Respimat® are collected descriptively and do not represent an objective of the NIS.

Following subgroup analyses will be performed for the primary objective:

- Patients with mMRC score ≥ 2 vs patients with mMRC score < 2 at baseline visit
- Patients < 65 years vs patients ≥ 65 years at baseline visit
- Patients with 0-1 exacerbations vs patients with ≥ 2 exacerbations requiring hospitalizations during the 12 months prior study inclusion
- Patients using Spiriva® HandiHaler® ≥ 1 year(s) vs patients on Spiriva® HandiHaler® < 1 year
- Patients with at least one concomitant disease that was classified as mental and/or cognitive disorder vs patients without any concomitant disease that was classified as mental and/or cognitive disorder
- Patients with GOLD spirometric classification 1/2 vs patients with GOLD spirometric classification 3/4 at baseline visit

Study design:	Open label, observational, non-interventional, national, multicenter study including COPD patients ≥ 40 years switching from Spiriva® HandiHaler® to Spiriva® Respimat® with an observational period of approximately 8 weeks (which is the average time between medical consultations). Patients will be followed-up to either discontinuation of Spiriva® Respimat® or up to week 52, whatever occurs first.
Population:	
COPD patients ≥ 40 years who are planned to be switched from Spiriva® HandiHaler® to Spiriva® Respimat®.
 
The decision to switch is made by the treating physician and patient according to patient's need and to the standard of best medical practice. This decision is made independently and prior to inclusion in this NIS.
 
Patients who will undergo a switch from Spiriva® HandiHaler® to Spiriva® Respimat® will be informed about the scope of the study and asked whether they would like to participate.

	
Inclusion criteria:
 
 Participants ≥ 40 years of age at baseline visit Patients with confirmed diagnosis of COPD* Patients who have been on Spiriva® HandiHaler® for ≥ 6 weeks at baseline visit Patients for whom a switch from Spiriva® HandiHaler® to Spiriva® Respimat® was planned prior to study inclusion. If additional inhalative COPD drugs (AICDs) are used: AICD treatment must have been stable for at least 6 weeks before study inclusion Signed written informed consent form to participation 
*Confirmed by spirometry: FEV1/FVC <0.7, (last available FEV1 and FVC including % predicted)
 
Exclusion criteria:
 
 Patients who have contraindications to Spiriva® Respimat® according to the current prescribing information label/ summary of product characteristics (SmPCs) Patients who have signs of a current, acute respiratory tract infection 2 weeks prior visit 1 Patients for whom further follow-up will not be possible at the enrolling site during the planned observational period (of approximately 8 weeks) Patients with confirmed diagnosis of only asthma Patients who had > 1 moderate to severe exacerbation(s) within the last 6 weeks prior to study inclusion Patients who are pregnant or breastfeeding Patients participating in an ongoing interventional study

Variables:	
Eligible patients who signed the informed consent form will undergo the baseline visit (= visit 1).
 
Visits are to be scheduled as per standard-of-care. Documentation at the sites is planned at baseline (month 0, visit 1) and after approximately 8 weeks after treatment start (visit 2). Patients will be requested to have an End-of Treatment (EoT) visit (Follow-up visit) if they discontinue Spiriva® Respimat® treatment or if they switch to another inhalative medication. Patients who are still on Spiriva® Respimat® will have a follow-up visit (visit 3) approximately 52 weeks after baseline visit. It is planned that each patient will have 3 visits during the 1-year observational period. Additional visits may be performed as needed, such as when COPD treatment requires adjustment, or whenever otherwise deemed necessary by the study physician based on usual care.

	Main data collected:
	
At baseline (visit 1):
 
• Patient demographics (age, gender, height, weight)• Concomitant diseases / comorbidities (relevant comorbidities such as cardiovascular diseases, diabetes mellitus type 2, depression, and diseases affecting the preparing and handling of the device)• Date of confirmed COPD diagnosis• Start with inhalative bronchodilators for COPD treatment [year]• Concomitant COPD medication including additional inhalative COPD drugs (AICDs, dosage, date of onset)• Breathlessness based on mMRC score• Last available FEV1 and FVC including % predicted (value and date measured, closest to the date of baseline visit)• Exacerbation history (number of moderate-to-severe exacerbations in the last 12 months before study inclusion, hospitalizations required)• Smoking history (number of pack years) and status (never, former, current) 
[REDACTED]
 
[REDACTED]
 
[REDACTED]
 
[REDACTED]

	
At visit 2:

	
• Breathlessness based on mMRC score
	
[REDACTED]

	
 CCQ score and the CCQ symptom, mental state, and functional state domain scores 
■ [REDACTED]
 
■ [REDACTED]
 
■ [REDACTED]
 
■ [REDACTED]
 
■ [REDACTED]
 
■ [REDACTED]
 
 Safety; ADR (serious and non-serious), fatal AEs, pregnancies 
At visit 3:
 
 Changes in COPD treatment scheme (yes/no, date, reason(s), kind of new treatment) Discontinuation of Spiriva® Respimat® treatment (date, reason(s)) Safety; ADR (serious and non-serious), fatal AEs, pregnancies (including exacerbations)
Data sources:	
To be completed by the physician:
 
 Patient demographics Patient medical files 
■ [REDACTED]
 
■ [REDACTED]
 
■ [REDACTED]
 
■ [REDACTED]
 
To be completed by the patient:
 
 mMRC breathlessness scale at baseline (visit 1) and visit 2 Health and functional status by CCQ at baseline (visit 1) and visit 2 
■ [REDACTED]

Study size:	
Primary endpoint:
 
Assuming 40% of high CCQ score patients have a 0.2 improvement in CCQ score from baseline at 8 weeks on treatment, then with a sample size of 100, the 95% CI for the response rate will be (0.304, 0.49)6.
 
Secondary endpoint:
 
Assuming 30% of all patients have a 0.2 improvement in CCQ score from baseline at 8 weeks on treatment, then with a total sample size of 200, the 95% CI for the response rate will be (0.236, 0.364).
 
With a dropout rate of 10% we would need a total of about 225 patients.

	
Sample size assumes that Respimat® is better compared to HandiHaler®. The sample size calculation/justification can only provide a rough estimate of the statistical power in such an exploratory real-world setting. Recruitment will continue until the minimum sample size is achieved.

Data analysis:	
Primary outcome: For the primary outcome, the percentage of patients with improvement will be presented together with the 95% confidence interval, whereupon improvement is defined as 0.2 points decrease in the CCQ score from baseline (visit 1) to visit 2.
 
Secondary outcomes: For secondary [REDACTED], the mMRC breathlessness scale at visit 1 and visit 2, [REDACTED] [REDACTED] Changes from visit 1 to visit 2 in the CCQ score and CCQ symptom, mental and functional state score as well as in the [REDACTED] [REDACTED]
 
Subgroup analyses on the primary objective will be performed for several stratifications as described before (see section Research question and objectives). If less than 20 patients are in one subgroup class, classes will be combined in a meaningful way, or the subgroup analysis will be omitted with reason.

Milestones:	
Estimated enrolment duration: 1 year First patient In (FPI): Q2/2022 Estimated individual observational period: at least 8 weeks, up to 52 weeks Last patient In (LPI): Q2/2023 Last patient Last visit (LPLV): Q2/2024 Final study report: July 2024

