8.2.2 Study population

Patients will be enrolled consecutively in the study. The decision to switch the patient from Spiriva® HandiHaler® to Spiriva® Respimat® will be made by the treating physician to the patient's need and to the standard of best medical practice prior to the inclusion into the study.

Patients with COPD planned to be switched according to the respective SmPC and consenting to participate in the study are eligible. To avoid any selection bias, all eligible patients will be invited to participate in this study, in the order in which their eligibility is determined. A time window of 1 years is foreseen for recruitment of the patients. Patients will be treated within clinical routine practice and according to the current standard of care. Patients who discontinue from treatment before the visit at week 52 will be asked to complete an EoT visit.

Inclusion criteria:

Patients can be included if all following criteria are met:

- Participants ≥ 40 years of age at baseline visit
- Patients with confirmed diagnosis of COPD*
- Patients who have been on Spiriva® HandiHaler® for ≥ 6 weeks at baseline visit
- Patients for whom a switch from Spiriva® HandiHaler® to Spiriva® Respimat® was planned prior to study inclusion. If additional inhalative COPD drugs (AICDs) are

used: AICD treatment must have been stable for at least 6 weeks before study inclusion

- Signed written informed consent form to participation

*Confirmed by spirometry: FEV1/FVC <0.7 (last available FEV1 and FVC including % predicted)

Exclusion criteria:

- Patients who have contraindications to Spiriva® Respimat® according to the current prescribing information label/ summary of product characteristics (SmPC)
- Patients who have signs of a current, acute respiratory tract infection 2 weeks prior visit 1
- Patients for whom further follow-up will not be possible at the enrolling site during the planned observational period (of approximately 8 weeks)
- Patients with confirmed diagnosis of only asthma
- Patients who had > 1 moderate to severe exacerbation(s) within the last 6 weeks prior to study inclusion
- Patients who are pregnant or breastfeeding
- Patients participating in an ongoing interventional study

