8.2.3 Study visits

Eligible patients who sign the informed consent form (ICF) will undergo the baseline visit.

Patients will be followed up over an observational period of approximately 52 weeks after baseline visit (visit 1). During the observational period, 2 further visits will be performed. Visit 2 will be approximately in week 8, visit 3 will be performed in week 52 as follow-up visit.

Patients who discontinue from the treatment before the visit at week 52 will be asked to complete an EoT visit.

[Figure 8.2.3:1](#) provides a study flow chart. [Table 8.2.3:1](#) gives an overview about the parameters collected during the study.

Figure 8.2.3:1 Study flow chart.

[figure not shown]

Table 8.2.3:1 Data collection parameters

Parameter	Baseline visit (Visit 1)	Visit 2 (approx. 8 weeks after baseline visit)	Visit 3 (approx. 52 weeks after baseline visit)/EoT visit (if Spiriva® Respimat® treatment is discontinued or switched)
Informed Consent Form	X		
Inclusion / Exclusion criteria	X		
Patient demographics (age [years], gender [m/f/d], height [cm], and weight [kg])	X		
Start of COPD (age at onset [years])	X		
Concomitant diseases / comorbidities (relevant comorbidities such as cardiovascular diseases, diabetes mellitus type 2, depression and diseases affecting the preparing and handling of the Respimat® device)	X		
Start of inhalative bronchodilators for COPD treatment [year]	X		
Concomitant COPD medication including additional inhalative COPD drugs (AICDs, dosage, date of onset [day-month-year]) up to 6 weeks before baseline visit	X		
Changes in COPD treatment scheme (date [day-month-year], reason(s))		X	X
Reason(s) for change from Spiriva® HandiHaler® to Spiriva® Respimat®	X		
Number of moderate to severe exacerbations in the last 12 months	X		
Number of exacerbations leading to hospitalization in the last 12 months	X		
mMRC breathlessness scale, completed by the patient	X	X	
Last available FEV1 and FVC (value and date measured [day-month-year])	X		
Respimat® training (yes/no)	X		

COPD severity based on GOLD assessment ¹	X		
GOLD spirometric classification, if available ²	X		
Smoking status [never/former/current]/history [number of pack years]	X		
Health and functional status by CCQ questionnaire, completed by patient	X	X	
[REDACTED]	■	■	
[REDACTED]	■	■	
Safety: Adverse Drug Reactions (serious and non-serious), fatal AE, pregnancy		X	X
Assessment of treatment start [yes/no], date of onset of treatment [day-month-year]		X	
[REDACTED]	■		

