8.3 VARIABLES

The following parameters will be collected and assessed at visit 1 and/ or visit 2 and/or visit 3:

- Patient demographics (age, gender, height & weight)
- Concomitant diseases / comorbidities (relevant comorbidities such as cardiovascular diseases, diabetes mellitus type 2, depression and diseases affecting the preparing and handling of the Respimat® device)
- Date of confirmed COPD diagnosis [year]
- Start with inhalative bronchodilators for COPD treatment [year]
- Concomitant COPD medication including AICDs (dosage, date of onset) up to 6 weeks before baseline visit
- Changes in COPD treatment scheme (date, reason(s))
- Last available FEV1 (value and date measured) and FVC including % predicted (value and date measured, closest to the date of baseline visit)
- Reported moderate-to-severe exacerbations based on medical history in the last 12 months and exacerbations leading to hospitalization in the last 12 months
- Smoking history (number of pack years) and status (never, former, current)
- Assessment of the severity of breathlessness based on the mMRC questionnaire
- GOLD spirometric classifications (1, 2, 3, 4) and GOLD patient groups (A, B, C, D) based on GOLD-2022
- Clinical control based on CCQ score and CCQ symptom, mental state, and functional state domain scores

- (Safety Reporting*; Adverse Drug Reactions (serious and non-serious), fatal AEs, and pregnancies at the beginning and at the end of the study)

*Safety data will be collected descriptively and are not a separate objective of the NIS.

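### Does the exacerbation subgroup leave patients with two or more exacerbations, but fewer than two hospitalised ones, without a class?

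*Combined protocol and SAP*

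**What the plan says.** The only definition visible in the available text is in the Abstract (section 3), under Research question and objectives: "Patients with 0-1 exacerbations vs patients with ≥ 2 exacerbations requiring hospitalizations during the 12 months prior study inclusion". It is one of six two-way splits listed for the primary objective, which is the responder proportion among patients with baseline CCQ of at least 2.

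The Data analysis entry of the Abstract says that subgroup analyses "will be performed for several stratifications as described before (see section Research question and objectives". It adds that a class with fewer than 20 patients is merged with another or the analysis is dropped. Section 7 of the body has the same title but, in the available text, lists no subgroups.

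Table 8.2.3:1 (section 8.2.3) has two separate baseline items: "Number of moderate to severe exacerbations in the last 12 months" and "Number of exacerbations leading to hospitalization in the last 12 months". Section 8.3 names both again: "Reported moderate-to-severe exacerbations based on medical history in the last 12 months and exacerbations leading to hospitalization in the last 12 months".

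Section 8.7 describes the whole analysis as descriptive and exploratory, without formal tests, and leaves full specification to an SAP issued before database lock. Section 8.7.2, which would fall between the main and the safety analysis, is not in this copy, so its content is unknown and cannot be counted as missing.

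**The concern.** A two-class subgroup should normally place every patient in exactly one class. Here the qualifier on hospitalisation is written once, next to the upper class, while two different 12-month counts are available. A patient with, say, three exacerbations and one admission is not in a class of 0-1 exacerbations, and is not in a class of at least two hospitalised ones either.

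Such patients can enrol. The only related exclusion in section 8.2.2 is "Patients who had > 1 moderate to severe exacerbation(s) within the last 6 weeks prior to study inclusion", which covers six weeks and not the year.

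If the word-by-word reading were programmed, some high-CCQ patients would drop out of this table and its two classes would not add up to the primary population. If the other reading were programmed, the same patients would sit in the lower class. The lower-class response rate, and the comparison drawn from it, would then depend on a choice that the line does not state.

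**Working it through.** **Step 1. Who changes class.** Let T be all exacerbations and H the hospitalised ones in the 12 months before inclusion, taking H ≤ T.

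| Pattern | Qualifier on upper class only | Qualifier on both classes |
|---|---|---|
| T = 0 or 1 | lower | lower |
| T ≥ 2, H = 0 or 1 | neither | lower |
| H ≥ 2 | upper | upper |

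The readings differ only in the middle row. The upper class is the same in both.

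**Step 2. Which reading the text favours.** The ending of the line is one run: the hospitalisation qualifier followed by the 12-month window. Nobody would leave the lower class without a look-back period, so the window has to reach back to it. The word-by-word reading therefore carries the end of the phrase back but not its beginning.

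The sibling lines help. Those on mMRC, age and airflow limitation end in a phrase that plainly serves both classes, for example "Patients with GOLD spirometric classification 1/2 vs patients with GOLD spirometric classification 3/4 at baseline visit". All five siblings are complementary splits, and 0-1 against at least 2 has the same form. With the qualifier on both classes the line becomes 0-1 against at least 2 hospitalised exacerbations. That is exhaustive and uses one item already in Table 8.2.3:1.

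**Step 3. The plan's own precision.** Section 8.5 assumes 100 high-CCQ patients and 40% response. The Wald half-width is 1.96 × √(0.40 × 0.60 / 100) = 0.096, giving 0.304 to 0.496, as printed. This result uses no subgroup.

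**Step 4. How far the lower-class rate could move.** The documents give no share for the middle row, so these inputs are assumptions: 20 of the 100 patients in the upper class (the smallest size reported as it stands), k patients in the middle row, and a response rate among them that differs by d = 0.20 from the rest of the lower class. With the qualifier on both classes the lower class has 100 − 20 = 80 patients; otherwise it has 80 − k. The difference between the two lower-class rates is (k / 80) × d.

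| k | Lower class, upper-only reading | Lower class, both-classes reading | Shift |
|---|---|---|---|
| 5 | 75 | 80 | 5/80 × 0.20 = 1.25 points |
| 10 | 70 | 80 | 10/80 × 0.20 = 2.5 points |
| 20 | 60 | 80 | 20/80 × 0.20 = 5.0 points |
| 30 | 50 | 80 | 30/80 × 0.20 = 7.5 points |

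For comparison, the half-width at 40% response is 1.96 × √(0.24 / 80) = 10.7 points with 80 patients and 1.96 × √(0.24 / 50) = 13.6 points with 50. Every shift is smaller.

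**Step 5. Whether the table would appear at all.** On both readings the upper class needs at least two hospitalised exacerbations in a year in 20 of the 100 patients. Below that, the small-class rule merges the classes or drops the analysis. Nothing in the documents shows that 20 will be reached.

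**The case for a change.** The strongest argument for a change is that the list does not settle the matter by itself. The line on mental and cognitive disorders writes out its whole qualifying clause a second time ("vs patients without any concomitant disease that was classified as mental and/or cognitive disorder"), so its author could have repeated the hospitalisation qualifier had it been meant for both classes.

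A third intention is also possible: overall frequency, 0-1 against at least 2 moderate-to-severe exacerbations. That would move the middle-row patients into the upper class and could decide whether the small-class rule applies. With an assumed 10 patients having two or more hospitalised exacerbations and 20 in the middle row, the upper class has 10 patients by the hospitalised count and 10 + 20 = 30 by the total count. The study is open label and the SAP is due only before database lock, so the choice could be made with outcome data in view.

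Part of this stands. The line is loosely worded, and repeating the qualifier would be harmless tidying. The rest is weaker. The mental and cognitive line has no shared ending, so it is a poor parallel. The third intention requires striking out the words on hospitalisation. The risk of a late choice presumes that neither section 8.7.2 nor the SAP names the count, and this copy cannot show that.

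**Conclusion.** No change to the plan follows. The definition is unclear, but it is not shown to be wrong. It is the kind of gap an analyst closes when programming the table: a count must be chosen, the natural choice is hospitalised exacerbations in both classes, and that choice leaves no patient unclassified. The alternative would still describe a clearly defined set of patients, provided the table states who is in it.

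The consequence is confined to the lower class of one of six exploratory subgroups. On the assumed inputs the shift is 1.25 to 7.5 percentage points against a half-width of about 10.7. The upper class is the same on both readings of the line, and the primary proportion, its interval and the sample size do not depend on it.

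This conclusion rests on the hospitalised count being a subset of the total count, on the assumed class sizes and 20-point difference, and on the descriptive status of the analysis in section 8.7. A change would also oblige the sponsor to choose between two different questions, hospitalised events or overall frequency, without any evidence in the documents that a reported result would otherwise be misleading.
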